10.4.1.3.2 Abnormal laboratory results and vital signs values

Not every laboratory or vital signs abnormality needs to be documented as AE. For clinically significant laboratory/vital signs abnormalities the following definitions and documentation rules apply:

- If a laboratory/vital signs abnormality is a sign of a disease or syndrome, the laboratory/vital signs abnormality is clinically significant and only the diagnosis of the causing disease or syndrome needs to be documented as AE.
- If a laboratory/vital signs abnormality results in specific symptoms but no diagnosis
 of a disease or syndrome can be made, the laboratory/vital signs abnormality is
 clinically significant and only the symptoms need to be documented as AEs.
- If a laboratory/vital signs abnormality is not a sign of a disease or syndrome and does not result in specific symptoms but leads to a change in trial treatment or in a medical intervention, the laboratory/vital signs abnormality is clinically significant and must be documented as AE.

10.4.1.3.3 AEs associated with an overdose or error in drug administration

An overdose is the accidental or intentional use of a drug in an amount (per administration or cumulatively) higher than the dose being studied (for the trial treatment) or higher than the maximum recommended dose according to the authorized product information (for approved concomitant medications). An overdose or incorrect administration of a drug is not itself an AE, but it may result in an AE.

All AEs associated with an overdose or incorrect administration should be documented as AE in source data and CRF and reported as SAE if applicable.

10.4.1.4 Suspected adverse reaction

Suspected adverse reactions are untoward and unintended responses to an IMP related to any dose administered.

The definition covers also medication errors and uses outside what is foreseen in the protocol, including misuse and abuse of the product.

Clinical Trial Protocol Trial number: BNT165-01 Page 68 of 82 Version: 4.0 Date: 13 FEB 2023

The definition implies a reasonable possibility of a causal relationship between the event and the IMP. This means that there are facts (evidence) or arguments to suggest a causal relationship.

10.4.2 Definition of SAE

A SAE is defined as any untoward medical occurrence that, at any dose:

- Results in death
- Is life-threatening

The term "life-threatening" in the definition of "serious" refers to an event in which the trial subject was at risk of death at the time of the event. It does not refer to an event, which hypothetically might have caused death, if it were more severe.

- Requires hospitalization or prolongation of existing hospitalization:
 - In general, hospitalization signifies that the trial subject has been detained (usually involving at least an overnight stay) at the hospital or emergency ward for observation and/or treatment that would not have been appropriate in the physician's office or outpatient setting. Complications that occur during hospitalization are AEs. If a complication prolongs hospitalization or fulfills any other serious criteria, the event is serious. When in doubt as to whether "hospitalization" occurred or was necessary, the AE should be considered serious.
 - Hospitalization for elective treatment of a pre-existing condition that did not worsen from baseline is not considered an AE.
- Results in persistent disability/incapacity:
 - The term disability means a substantial disruption of a person's ability to conduct normal life functions.
 - This definition is not intended to include experiences of relatively minor medical significance such as uncomplicated headache, nausea, vomiting, diarrhea, influenza, and accidental trauma (e.g., sprained ankle) which may interfere with or prevent everyday life functions but do not constitute a substantial disruption.
- Is a congenital anomaly or birth defect.
- · Other situations:
 - Medical or scientific judgment should be exercised in deciding whether SAE reporting is appropriate in other situations such as important medical events that may not be immediately life-threatening or result in death or hospitalization but may jeopardize the trial subject or may require medical or surgical treatment to prevent one of the other outcomes listed in the above definition. These events should usually be considered serious. Examples of such events include invasive or malignant cancers, intensive treatment in an emergency room or at home for allergic bronchospasm, blood dyscrasias or convulsions that do not result in hospitalization, or development of drug dependency or drug abuse.

Clinical Trial Protocol Trial number: BNT165-01 Page 69 of 82 Version: 4.0 Date: 13 FEB 2023

 For real time monitoring of events which may contribute to the pausing rules criteria, all such AEs (Grade 3 or higher possibly related) need to be reported on an expedited timeline (within 24 h) like that of an SAE.

10.4.2.1 Use of the terms "severe" and "serious"

The terms "severe" and "serious" are not synonymous. Severity refers to the intensity of an AE (e.g., rated as mild, moderate severe or potentially life-threatening, as described in the US FDA "Toxicity Grading Scale for Healthy Adult and Adolescent Volunteers Enrolled in Preventive Vaccine Clinical Trials"); see Section 10.4.3 for guidance on the assessment of severity; the event itself may be of relatively minor medical significance (such as severe headache without any further findings).

Severity and seriousness need to be assessed independently for each AE recorded on the CRF.

SAEs must be reported by the investigator to the sponsor within 24 h after learning of the event; see Section 10.4.4 for reporting instructions.

10.4.2.2 SAE exemptions

In general, SAEs are defined according to ICH Topic E2A (CPMP/ICH/377/95), EU Directive 2001/20/EC and ENTR/CT-3 (see Section 10.4.2). In the present trial, some events are excluded from the SAE definition. The following events do not need to be reported as SAEs:

- AEs and SAEs occurring after the end of the observation period must only be reported by the investigator to the sponsor if a relationship to trial treatment or trial procedure is suspected.
- Hospitalizations that were necessary solely because of trial subject requirement for care outside of normal outpatient clinic operating hours will not be considered as reportable SAE.
- Hospitalizations for procedures or interventions of a pre-existing condition of the trial subject (elective surgery = planned, non-emergency surgical procedure) will not be considered as a reportable SAE (unless the intervention/procedure is not caused by an acute worsening of the pre-existing condition during the time trial participation):
 - if it was planned and documented in trial subject record before the trialspecific trial subject informed consent was signed (ICF for trial participation, see Section 10.1.3), or
 - if it was scheduled during the trial when elective surgery became necessary, and the trial subject has not experienced an AE.
- Routine treatment or monitoring of an underlying disease not associated with any deterioration in the trial subject's condition.

Page 70 of 82 Version: 4.0 Date: 13 FEB 2023

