10.4.1 Definition of AE

AE definition:

- An AE is any untoward medical occurrence in a trial subject administered a
 pharmaceutical product and which does not necessarily have to have a causal
 relationship with this treatment.
- NOTE: An AE can therefore be any unfavorable and unintended sign (including an abnormal laboratory finding), symptom, or disease (new or exacerbated) temporally associated with the use of a medicinal product, whether or not considered related to the medicinal product.
- Medically attended adverse event is an AE for which the subjects received medical attention defined as hospitalization, or an otherwise unscheduled visit to or from medical personnel for any reason, including emergency room visits.

10.4.1.1 Events meeting the AE definition:

- Any abnormal laboratory test results (hematology or clinical chemistry) or other safety assessments (e.g., ECG, vital signs measurements), including those that worsen from baseline, considered clinically significant in the medical and scientific judgment of the investigator.
- Exacerbation of a chronic or intermittent pre-existing condition including either an increase in frequency and/or severity of the condition.
- Serious AEs occurring after the date informed consent was given (ICF signed and dated) and AEs (non-serious AEs) occurring after first IMP administration.
- Signs, symptoms, or the clinical sequelae of a suspected drug-drug interaction.
- Signs, symptoms, or the clinical sequelae of a suspected overdose of either trial treatment or a concomitant medication. Overdose per se will not be reported as an AE/SAE.

10.4.1.2 Events not meeting the AE definition:

- Any clinically significant abnormal laboratory findings or other abnormal safety assessments which are associated with an underlying disease, unless judged by the investigator to be more severe than expected for the trial subject's condition.
- Medical or surgical procedure (e.g., endoscopy, appendectomy): the condition that leads to the procedure is the AE.
- Situations in which an untoward medical occurrence did not occur or continue (social and/or convenience admission to a hospital).
- Anticipated day-to-day fluctuations of pre-existing disease(s) or condition(s) present or detected at the start of the trial that do not worsen.

Page 67 of 82 Version: 4.0 Date: 13 FEB 2023

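### A double negative in the SAE exemption for elective procedures reverses its own exception

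*Protocol*

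**What the plan says.** Section 10.4.2.2 of the protocol lists events that need not be reported as SAEs. One bullet covers hospitalizations for procedures on a pre-existing condition, limited by its own definition to "elective surgery = planned, non-emergency surgical procedure". The default is that such an admission "will not be considered as a reportable SAE". A parenthesis gives the exception: "unless the intervention/procedure is not caused by an acute worsening of the pre-existing condition during the time trial participation". Two alternative conditions follow. The first begins "if it was planned and documented in trial subject record before the" and refers to the signing of consent. The second reads "if it was scheduled during the trial when elective surgery became necessary, and the trial subject has not experienced an AE".

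Two other protocol sections deal with the same situation. Section 10.4.2 makes an event serious if it "Requires hospitalization or prolongation of existing hospitalization", and adds: "Hospitalization for elective treatment of a pre-existing condition that did not worsen from baseline is not considered an AE". Section 10.4.1.1 counts as an AE: "Exacerbation of a chronic or intermittent pre-existing condition including either an increase in frequency and/or severity of the condition".

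The SAP (section 8.5.4 and its subsections) tabulates SAEs as collected. It describes no step that would recover an event wrongly left out of SAE reporting.

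**The concern.** The rule reads: not reportable, unless not caused by acute worsening. The exception therefore applies when there was no worsening and fails to apply when there was. One would expect the clause to do the reverse and bring back into SAE reporting those planned procedures that were in fact prompted by a deterioration during the trial.

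SAE status has consequences here. The proportion of subjects with at least one SAE up to 24 weeks after Dose 3 is a primary estimand (protocol section 3). A possibly related SAE with no plausible alternative cause pauses dosing in the affected and higher cohorts (section 7.1.1). The situation can arise, because inclusion criterion 4 admits volunteers with stable pre-existing disease. Section 8.3.6 also says that the exemptions of 10.4.2.2 apply to fatal cases.

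**Working it through.** The protocol gives no figure for this point, so the check is mainly one of logic.

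**Step 1: the literal rule.** Let W mean that the procedure was caused by acute worsening during the trial. The text says: not reportable unless not-W. Hence W gives exempt, and not-W gives reportable.

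**Step 2: comparison with the other sections, case by case.**

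| Case | 10.4.2.2 read literally | 10.4.1.1 and 10.4.2 |
|---|---|---|
| Emergency admission for acute worsening | Bullet does not apply | SAE: exacerbation is an AE, admission makes it serious |
| Non-emergency procedure planned and documented before consent, then done because of acute worsening | Exempt | SAE, for the same reason |
| Non-emergency procedure scheduled during the trial because of acute worsening | Not exempt: the second condition requires that no AE occurred, and the worsening is an AE | SAE |
| Planned elective admission without worsening | Reportable | Not an AE |

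The texts conflict in the second and fourth rows. The second row is under-reporting and the fourth is over-reporting. In the first and third rows other text already gives the expected answer.

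**Step 3: is the wording corrected elsewhere?** No current text in the protocol or SAP does so. The last bullet of 10.4.2.2 exempts only routine care without deterioration, which agrees with 10.4.2 and not with the parenthesis.

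**Step 4: scale of one event.** Each cohort has 16 vaccine and 4 placebo subjects (section 4.1.1), and the SAP pools placebo (section 8.1).
- Vaccine group: 1/16 = 6.25 percentage points.
- Combined placebo: 1/(3 × 4) = 1/12 = 8.3 percentage points.

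**Step 5: how long SAE reporting is the scheduled route.** AEs and MAAEs are collected until 28 d after each dose, and SAEs until Visit 14 (section 8.3.1). Doses fall on Days 1, 57 and 183, and Visit 14 is 365 d after Dose 3. Using nominal days:
- Dose 1 to Visit 14: (183 − 1) + 365 = 547 days.
- AE and MAAE windows: 3 × 28 = 84 days.
- Outside the windows: 547 − 84 = 463 days, and 463/547 = 85%.
- For the primary SAE estimand, which ends 24 weeks (168 d) after Dose 3: 182 + 168 = 350 days, of which 350 − 84 = 266 (76%) lie outside the windows.

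**The case against.** The strongest reply is that the intended meaning is plain. Taken literally, the parenthesis would make ordinary planned surgery without worsening reportable, which would empty both conditions of the bullet and contradict 10.4.2. Many investigators would read past the slip. That stands as evidence of intent and shows that this is a drafting error. It does not remove the problem: 10.4.2.2 is the specific rule on what need not be reported, and a site following it to the letter would be complying with the protocol.

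A reader might infer that any admission caused by acute worsening is exempt. The documents do not support that. The bullet covers only non-emergency procedures that meet one of two conditions, and the second condition fails when the worsening is an AE.

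A reader might also infer that the event would escape the 24-h report and the Internal Review Committee (IRC). That is too strong. Possibly related AEs of Grade 3 or higher go to the sponsor within 24 h whether or not they are serious (sections 7.1, 8.3.2 and 10.4.2). Related Grade 4 AEs, related immune-related AEs, and two similar related AEs of Grade 3 or higher each trigger a pause without SAE status. The IRC may also meet ad hoc on a single AE. For pausing, the remaining gap is a related Grade 1 or 2 event, or a single related Grade 3 event that meets no other rule.

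Nor would the event necessarily go unrecorded. Within 28 d of a dose the exacerbation is still an AE, and an admission for it falls within the MAAE definition.

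Finally, frequency will be low. Inclusion criterion 4 requires stable disease over the 90 days before screening, and exclusion criterion 6 removes many chronic conditions. This also stands.

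**Conclusion.** The text is wrong as written: an internal inconsistency with low expected frequency. The parenthesis in 10.4.2.2 reverses the exception and conflicts with 10.4.2 and 10.4.1.1. Its practical reach is one case of under-reporting (a non-emergency procedure planned before consent and then done because of acute worsening) and one of over-reporting (a planned admission without worsening).

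The consequence is misclassification of SAEs, which feed a primary estimand and the pausing rules. It weighs most outside the 28-day windows, where a wrongly exempted event could leave no AE, MAAE or SAE record. The percentage-point figures show the effect of a single event and say nothing about its likelihood, for which the documents give no rate. The day counts assume nominal visit timing and all three doses given.

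**What to change.** Delete the word 'not' from the parenthesis in protocol section 10.4.2.2, so that the exemption is lost when the procedure is caused by acute worsening of the pre-existing condition during the trial. This brings the bullet into line with 10.4.2 and 10.4.1.1 and removes both misclassifications. If site instructions for the SAE form repeat the sentence, correct them too.

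The cost is one word. Because it alters the protocol, it has to go through an amendment with ethics committee submission (section 10.1.1), and it could be included with other changes. The SAP needs no change.

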10.4.3 Recording and follow-up of AEs and/or SAEs

AE and SAE recording

The investigator needs to assess and document any AE regardless of association with the use of the trial treatment during the period of observation (see Section 8.3.1).

- Data pertaining to AEs will be collected during each trial visit. Based on the trial subject's spontaneous description or investigator's inquiry or discovered in the course of examinations done during the visit, clinical significance of any sign or symptom needs to be evaluated by the investigator.
- Clinically significant findings need to be documented as AEs in the source data and CRF. Findings that are evaluated and documented in the source data as not clinically significant (e.g., an abnormal laboratory value without any clinical manifestation), should not be documented as AE.
- The investigator will then record all relevant AE information in the CRF and perform an assessment on:
 - Severity (see the section Assessment of severity)
 - Seriousness
 - Outcome
 - Causal relationship of the AE to the trial treatment/trial procedure
 - Any trial treatment action and/or any other action taken
 - All assessments as well as AE term (diagnosis/description), start date and time of onset, end date and time need to be documented in the CRF.
 - There may be instances when copies of medical records for certain cases are requested by the sponsor. In this case, all trial subject identifiers, with the exception of the subject number, will be redacted on the copies of the medical records before submission to the sponsor.
 - To avoid colloquial expressions, the AE should be reported in standard medical terminology. The investigator will attempt to establish a diagnosis of the event based on signs, symptoms, and/or other clinical information. Whenever possible, the diagnosis (not the individual signs/symptoms) will be documented as the AE. If a definitive diagnosis is not possible, the individual signs and symptoms should be recorded.

Assessment of severity

The assessment of AE and/or SAE intensity should be done consistently for all trial subjects treated with the same treatment and dose. In case of doubt, the trial Medical Monitor should be consulted.

The intensity of (serious) AEs will be graded by the investigator. For further guidance refer to the US FDA "Toxicity Grading Scale for Healthy Adult and Adolescent Volunteers

Clinical Trial Protocol Trial number: BNT165-01 Page 71 of 82 Version: 4.0 Date: 13 FEB 2023

Enrolled in Preventive Vaccine Clinical Trials". Where specific guidance for an adverse event term is not provided, the following general approach should be followed:

- Grade 1 Mild; does not interfere with the trial subject's usual function.
- Grade 2 Moderate; interferes to some extent with the trial subject's usual function.
- Grade 3 Severe; interferes significantly with the trial subject's usual function.
- Grade 4 Potentially life-threatening; life-threatening consequences, urgent intervention required.

With regards the intensity of an (serious) AE, the following needs to be documented and CRF:

- Initial intensity of the AE
- · For each change of intensity:
 - New grade of intensity
 - Date of change (= start of new grade of intensity)
 - Time of change (only if relevant)
 - New action taken

A change of severity only needs to be documented if there is a clearly definable change in grading of the AE (e.g., a laboratory result changes from severe to moderate).

An event is defined as "serious" when it meets at least one of the predefined seriousness criteria as described in the definition of an SAE, independent from its intensity.

Actions taken by the investigator

Actions taken by the investigator as a result of an AE must be documented.

Action(s) taken with trial treatment (IMPs) by the investigator:

- Dose not changed (= continuation of trial treatment administration according to the trial protocol)
- Dose reduced (= reduction of the trial treatment dosage *)
- Drug interrupted (i.e., trial treatment withdrawn temporarily, interruption and resumption); i.e.:
 - Delayed administration of IMP dose
 - Delayed start of the next IMP dose
 - Cancellation of IMP administration at a given visit
 - Interruption of IMP administration during a given visit
- Drug withdrawn (i.e., trial treatment permanently withdrawn)
- Unknown (e.g., in case the trial subject is lost to follow-up)
- Not applicable (e.g., in case treatment with trial treatment has not yet started or event starts after last trial treatment administration)

Clinical Trial Protocol Trial number: BNT165-01 Page 72 of 82 Version: 4.0 Date: 13 FEB 2023

*If an increase of trial treatment dosage is intended according to the trial protocol and the dosage is kept in comparison to last administration of trial treatment, it needs to be documented as "Dose reduced."

Other action(s) that may be taken by the investigator include:

- None
- Initiation of a remedial (concomitant) therapy
- Other specific treatment(s) of AE (to be specified)

Investigator assessment of the outcome of an AE

The investigator has to assess the outcome of an AE (and not the trial subject's outcome) at the time of documentation based on the following criteria:

- Recovered/resolved* (= complete resolution of the AE)
- Recovering/resolving (= AEs which are improving but not yet resolved completely, e.g., decreases in severity grade)
- Not recovered/not resolved (= AEs which are ongoing without improving or still present when the trial subject deceases due to another cause)
- Recovered/resolved with sequelae* (= trial subject recuperated but retained pathological conditions resulting from the AE; the sequelae should be indicated)
- Fatal** (= death due to the AE)
- Unknown (e.g., in case the trial subject is lost to follow-up)
- * Generally, an AE is defined as recovered/resolved if all symptoms have ceased, no medication for treatment of the event is taken anymore and no other measures (e.g., hospitalization) are ongoing.

If the trial subject has developed permanent or chronic symptoms or if the event requires long-term medication(s), the AE is defined as recovered/resolved with sequelae as soon as no changes of symptoms and/or medication(s) are expected anymore.

An AE that is documented as a worsening of a medical condition already known at baseline, is defined as recovered as soon as the medical condition has returned to baseline status.

** In case of a fatal event, the event term should not be "death" but the underlying event which led to death (death = outcome). If there is more than one AE in a fatal case, only the AE leading to death will be attributed with the outcome "fatal". All other AEs ongoing at the time of death will be attributed with the outcome "not recovered/not resolved". A copy of an autopsy report should be submitted if available.

Assessment of causality

The investigator is obligated to assess the relationship between each occurrence of each SAE and trial treatment and/or trial procedure.

The investigator will use clinical judgment to determine the relationship.

Clinical Trial Protocol Trial number: BNT165-01 Page 73 of 82 Version: 4.0 Date: 13 FEB 2023

Alternative causes, such as underlying disease(s), concomitant therapy, and other risk factors, as well as the temporal relationship of the event to trial treatment administration will be considered and investigated.

It is sufficient to document the causality in the source data and CRF as:

- Related (= there is a reasonable possibility of a causal relationship) or
- Not related (= there is no reasonable possibility of a causal relationship)

The relationship or association of an AE or SAE to a trial treatment/trial procedure will be assessed by the investigator after having evaluated all accessible data and, if necessary, he/she will re-evaluate the case as new information becomes available.

Events caused by the procedure of trial treatment administration should be differentiated from events caused by the trial treatment itself. Only events suspected to be caused by the IMPs itself should be documented as suspected adverse reactions but not events caused by the procedure of trial treatment administration.

In this trial, it cannot be excluded that during the course of the trial some procedures give rise to AEs which are related to the trial procedure and not to the trial treatment. Procedure-related AEs can occur on the site of injection of the trial treatment (e.g., redness, swelling, hematoma or itching) or during or after trial-specific procedure (e.g., discomfort after blood drawing). These events must be reported in the CRF on Adverse Event pages as "related to trial procedure" with the causing procedure specified.

Notes applicable for relationship to trial procedures including trial treatments

There may be situations in which an SAE has occurred, and the investigator has minimal information to include in the initial report to the sponsor. However, it is very important that the investigator always makes an assessment of causality for every event before the initial transmission of the SAE data to the sponsor.

The investigator may change their opinion of causality in light of follow-up information and send a SAE follow-up report with the updated causality assessment.

The causality assessment is one of the criteria used when determining regulatory reporting requirements.

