3 OBJECTIVES AND ENDPOINTS

3 OBJECTIVES AND ENDPOINTS					
OBJECTIVES	ESTIMANDS	ENDPOINTS			
Primary objectives					
To describe the safety and tolerability of BNT165b1 vaccination in healthy adults.	 For each DL cohort: Frequency of solicited local reactions at the injection site recorded up to 7 d after each dose. Frequency of solicited systemic reactions recorded up to 7 d after each dose. Proportion of subjects with at least one AE occurring up to 28 d after each dose. Proportion of subjects with at least one MAAE occurring up to 28 d after each dose. Proportion of subjects in each cohort with at least one SAE occurring up to 24 weeks after Dose 3. 	 Solicited local reactions (pain, erythema/redness, induration/swelling) Solicited systemic reactions (vomiting, diarrhea, headache, fatigue, myalgia, arthralgia, chills, and fever) AEs SAEs MAAEs 			
Exploratory objectives					
To describe the humoral immune responses induced by BNT165b1 vaccination at different DLs in healthy adults.	Not applicable	Levels of antigen-specific serum and/or plasma antibodies (total IgG) measured using ELISA and/or similar assays CCI			
CCI					

Page 26 of 82 Version: 4.0 Date: 13 FEB 2023

Abbreviations: AE = adverse event; CCI d(s) = day; DL(s) = dose level(s); ELISA = enzyme-linked immunosorbent assay; IgG = immunoglobulin G; MAAE = medically attended adverse event; SAE = serious adverse event.

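### Protocol 10.4.3 can be read as a clinical-significance test for any symptom before it is recorded as an AE, against 10.4.1 and 8.3.2; mild unsolicited symptoms could be left out of the primary AE proportion

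*Protocol*

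**What the plan says.** Protocol Section 10.4.3, under AE and SAE recording, covers what the subject volunteers, what the investigator asks about and what examinations show. For all three it says that the "clinical significance of any sign or symptom needs to be evaluated by the investigator". It continues: "Clinically significant findings need to be documented as AEs in the source data and CRF". It then deals with the rest: "Findings that are evaluated and documented in the source data as not clinically significant" are not to be entered as AEs. The one example given is a laboratory value with no clinical manifestation.

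Section 10.4.1 defines an AE without any such condition: "An AE is any untoward medical occurrence in a trial subject administered a" pharmaceutical product, and "An AE can therefore be any unfavorable and unintended sign (including an abnormal laboratory finding), symptom, or disease". Section 10.4.1.1 brings in the words "considered clinically significant in the medical and scientific judgment of the investigator" only for abnormal laboratory results and other safety assessments, with ECG and vital signs as examples.

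The estimand that depends on these entries is primary (Protocol Section 3): "Proportion of subjects with at least one AE occurring up to 28 d after each dose". SAP Section 8.5.4.1 builds it from events entered on the Adverse Events page of the eCRF with onset in the window.

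**The concern.** A symptom that a subject describes or reports when asked is not a test result, so the 10.4.3 sequence reaches beyond the laboratory and assessment findings to which 10.4.1.1 confines the significance test. No section says what clinical significance means for a symptom. Two sites could therefore treat the same day of mild nausea differently, and each could point to protocol text in support.

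At stake is whether mild unsolicited symptoms are captured consistently in a primary count with small denominators. Some symptoms that Section 12.1 expects after RNA vaccines, such as nausea and lymphadenopathy, are not on the solicited list in Section 3. They reach the primary analysis only as unsolicited AEs. The same holds for any symptom that begins after the 7-day diary closes. The trial is multi-center and cohorts open one after another. If the threshold for recording did vary, the variation could follow site or dose level.

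**Working it through.** **Step 1. Which rule applies to a mild symptom?**

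| Protocol section | Rule for a mild symptom |
|---|---|
| 10.4.3, recording steps | Judge significance of signs and symptoms; do not enter findings judged not significant |
| 10.4.3, opening sentence | Assess and document any AE, related or not |
| 10.4.1 | An untoward symptom can be an AE; no significance condition |
| 10.4.1.1 | Significance condition for laboratory and other safety assessments only |
| 10.4.1.3.2 | Significance rules for laboratory and vital-sign abnormalities only; where these cause symptoms without a diagnosis, the symptoms are the AEs |
| 8.3.2 | Record every AE that is seen or volunteered; no test stated |
| 10.4.1.3.1 | Vomiting with mild, untreated dehydration is recorded as an AE (vomiting) |
| 10.4.2.1 | An AE can be medically minor |
| 10.4.3, severity | Grade 1 exists: "Grade 1 Mild; does not interfere with the trial" subject's usual function |
| 10.4.3, causality | Procedure-related events such as itching, or discomfort after a blood draw, go on the AE pages |

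Only the first row supports screening symptoms out. The others either record minor symptoms or confine the test to assessments. The text is in conflict, and the weight of it favors recording.

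**Step 2. Can the analysis recover an omitted symptom?** No. SAP 8.5.4.1 counts eCRF AE-page entries. Wellbeing-call data (SAP 8.5.8) and delayed injection-site reactions (SAP 8.5.2) are listed only.

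**Step 3. Effect of one omission.** Each cohort has 16 vaccine recipients (Protocol 9.2), and AE percentages use the number in the analysis set (SAP 8.1). One vaccinee with no other AE therefore counts 1/16 = 6.25 points. Placebo is pooled over three cohorts of 4, so one placebo subject counts 1/12 = 8.3 points.

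**Step 4. The plan's own figure.** Protocol 9.2 gives the probability of at least one AE in 20 subjects as 88% at a 10% rate and 96% at 15%. With 1 − (1 − p)^n:

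- 1 − 0.90^20 = 87.8%
- 1 − 0.85^20 = 96.1%

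Both reproduce. For the 16 vaccinees alone they are 81.5% and 92.6%. That difference is a separate matter.

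**Step 5. Illustration under assumption.** Let f be the share of subjects with an AE whose only AEs go unrecorded. The documents give no value for f or for the true rate p. The recorded proportion is p(1 − f), and the chance of at least one record among 16 is 1 − (1 − p(1 − f))^16.

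| True p | f = 0 | f = 25% | f = 50% | f = 75% |
|---|---|---|---|---|
| 10%: chance of at least one record | 81.5% | 71.3% | 56.0% | 33.3% |
| 15%: chance of at least one record | 92.6% | 85.2% | 71.3% | 45.8% |
| 30%: recorded proportion | 30% | 22.5% | 15% | 7.5% |
| 50%: recorded proportion | 50% | 37.5% | 25% | 12.5% |

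The table shows how the count responds to f. It is not evidence about what f would be.

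**The case against.** The best defense is that 10.4.3 contains loose wording and no real filter. The sentence that excludes items speaks of findings, and its only example is a laboratory value without clinical manifestation; a symptom is itself a clinical manifestation. The section opens by requiring any AE to be documented, and where no diagnosis is possible it asks for the individual signs and symptoms. With 8.3.2, the vomiting example, the Grade 1 category and the procedure-related examples, an investigator reading the whole protocol would probably record mild symptoms.

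Most of this stands. A reader might infer that every symptom must pass the test, but the documents do not support so firm a reading. The defense does not remove the words about any sign or symptom, or the step from that judgment to what is and is not entered. The example is only an example. A site that applied those steps literally would still be following the protocol.

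Three limits also stand:

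- Solicited reactions in Days 1 to 7 go into the e-diary, are graded from Grade 1 and have their own primary estimands. They bypass this rule unless serious or continuing past Day 7.
- Investigators are blinded (Protocol 6.3.2.2), so different screening of vaccine and placebo within a cohort is unlikely.
- No hypothesis is tested, and the Grade 3 or higher pausing criterion does not depend on Grade 1 entries.

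**Conclusion.** The recording rules for mild symptoms conflict, and the conflict bears on a primary estimand. Under the literal reading of 10.4.3, a mild unsolicited symptom can be left off the only page from which the AE proportion is built. Each omitted vaccinee with no other AE costs 6.25 points at that dose level, assuming all 16 are dosed.

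A reader might go further and conclude that the reported proportion is biased downward, or substantially so because most unsolicited symptoms are mild. The documents support neither. Downward bias arises only if sites adopt the stricter reading, and nothing shows that they do. The documents do not give the grade distribution of unsolicited symptoms. Variation between sites or successive cohorts is likewise a possibility and not a finding. Neither the likelihood nor the total size of the effect can be derived.

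This is a defect in collection wording. It changes no SAP method and no sample-size figure. It is worth correcting because the correction is cheap and removes a site-dependent entry rule from a primary count.

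**What to change.** In Protocol 10.4.3, limit the clinical-significance judgment to laboratory, ECG, vital-sign and other safety-assessment findings, in line with 10.4.1.1. Add that untoward symptoms or illnesses reported within the collection window are recorded as AEs and graded, Grade 1 included, whatever their clinical significance. Make this subject to three existing rules, which should stay as they are: recording the diagnosis in place of its symptoms (10.4.3), secondary events (10.4.1.3.1), and solicited events held in the e-diary. Carry the same wording into the CRF completion guidance.

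If AE collection has already ended, state in the clinical trial report which rule the sites applied.

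The cost is protocol and CRF-guidance wording. The downside is somewhat more Grade 1 entries and slightly higher reported AE proportions.
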